3.0 Endpoints

3.1 Primary Endpoint(s)

[figure not shown]
The primary endpoint is the responder status of *Mostly satisfied* or *Very satisfied* on the Facial Line Satisfaction Questionnaire (FLSQ) Follow-up Item 4 at Day 30.

[figure not shown]
3.2 Secondary Endpoint(s)

[figure not shown]
The secondary endpoint is

- Change from baseline in subject's assessment based on Rasch-transformed score of FACE-Q Psychological Function scale at Day 30

3.3 Additional Endpoint(s)

3.4 Safety Endpoint(s)

- The safety endpoint is the incidence of adverse events (AEs).

4.0 Analysis Populations

The following population sets will be used for the analyses.

The Modified Intent to Treat (mITT) Population includes all enrolled subjects who receive the total dose of 64 U of BOTOX Cosmetic, as described in the study protocol. The mITT Population will be used for all efficacy analyses. The Safety Analysis Set (also referred to as the Safety Population) consists of all subjects who receive at least 1 injection of study drug. The safety analyses will be based on the Safety Population.

5.0 Subject Disposition

The total number of subjects who were screened, enrolled and treated will be summarized.

A summary of subject accountability will be provided where the number of subjects in each of the following categories will be summarized:

- Number of subjects screened
- Number of subjects treated
- Number of subjects completed the study
- Number of subjects discontinued from the study
 - Reasons for discontinuation from the study

The number of subjects in each analysis population will also be summarized.

6.0 Study Drug Duration

For the Safety Population, study duration will be summarized with descriptive statistics (mean and standard deviation, median, Q1, Q3, minimum, and maximum). The number of subjects followed for specific periods of time (1-30 days, 31-60 days, 61-90 days, and 91-120 days, 121-150 days, 151 days to 180 days, >180 days) will also be summarized. Study duration will be calculated as date of end of study participation minus date of study drug administration +1.

7.0 Subject Characteristics

Demographics, baseline characteristics, medical history, prior and concomitant medications, and prior and concurrent procedure will be summarized for the mITT population. Categorical variables will be summarized with the number and percentage of subjects; percentages will be calculated based on the number of non-missing observations. Continuous variables will be summarized with descriptive statistics (number of non-missing observations, mean and standard deviation, median, minimum, and maximum).

7.1 Demographics and Baseline Characteristics

Demographic and baseline characteristics will be summarized descriptively for the mITT population. Unless otherwise specified, baseline is defined as the last non-missing value prior to the first administration of study treatment.

Continuous demographic variables include age, weight, height and BMI.

Categorical demographic variables include:

- Sex reported at birth
- Sex
- Gender identity
- Ethnicity (Hispanic or Latino, Not Hispanic or Latino)
- Race
- Fitzpatrick skin type (I, II, III, IV, V, VI)
- Prior Botulinum Toxin Treatment

Baseline characteristics include investigator-rated and subject-rated GL severity at maximum contraction and at rest using AGLSS, investigator-rated and subject-rated LCL at maximum contraction and at rest using LCLSS, investigator-rated and subject-rated FHL at maximum contraction and at rest using FHLSS, FLSQ baseline impact domain score and FACE-Q baseline Psychological Function score.

7.2 Medical History and Prior and Concomitant Medication

Medical history data will be coded using the current Medical Dictionary for Regulatory Activities (MedDRA). The actual version of the MedDRA coding dictionary will be noted in the statistical tables. The number and percentage of subjects in each medical history category (by MedDRA system organ class and preferred term (PT)) will be summarized. The system organ class (SOC) will be presented in alphabetical order, and the preferred terms will be presented in alphabetical order within each SOC. Subjects reporting more than one condition/diagnosis will be counted only once in each row (SOC or PT).

A prior medication is defined as any medication taken prior to the date of the first study drug administration. A concomitant medication is defined as any medication that started prior to the date of the first study drug administration and continued to be taken after the first study drug administration or any medication that started on or after the date of the first study drug administration. Prior and concomitant medications will be summarized separately for the mITT Population. The number and percentage of subjects taking prior and concomitant medications will be summarized by generic drug name, based on the World Health Organization (WHO) Drug Dictionary. The actual version of the WHO Drug Dictionary will be noted in the statistical tables.

7.3 Prior and Concurrent Procedures

All procedures undergone prior to the date of the study drug administration will be considered as prior procedures. All procedures undergone on or after date of the study drug administration through the exit visit will be considered concurrent procedures. Prior and concurrent procedures will each be summarized by MedDRA High Level Term (HLT) and PT for the mITT Population. The MedDRA HLT will be presented in alphabetical order, and the PTs will be presented in alphabetical order within each HLT.

7.4 Protocol Deviations

Protocol deviations are defined in accordance with ICH guidelines and include but are not limited to: eligibility criteria violations, receipt of wrong treatment or incorrect dose of

study treatment, development of withdrawal criteria without being withdrawn, and the use of excluded concomitant medications. A listing of subjects with protocol deviations will be provided.

For all protocol deviation categories and across all categories, the number and percentage of randomized subjects with at least one protocol deviation will be summarized.

8.0 Handling of Potential Intercurrent Events for the Primary and Key Secondary Endpoints

Observed data will be used without imputation, so subjects who have an intercurrent event resulting in not having FLSQ Item 4 at Day 30 for any reason will not be included in the primary efficacy endpoint. Intercurrent events include:

- Subjects who are enrolled but do not receive any study drug;
- Subjects who are enrolled and treated but prematurely discontinue the study before assessment of the primary endpoint;
- Subjects who die before assessment of primary endpoint;
- Subjects who are lost to follow-up and are missing assessment of primary endpoint;
- Subjects who are missing assessment of primary endpoint for any other reason (including COVID) not mentioned above
 - The same approach will be used for the secondary analysis.

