3 OBJECTIVES AND ENDPOINTS

3.1 Objectives, Hypotheses, and Estimands

Objective

The objective of this study is to evaluate subject satisfaction and natural outcomes following the administration of 64 U of BOTOX Cosmetic in subjects with upper facial lines (GL, LCL, and FHL).

Clinical Hypothesis

Single treatment of upper facial lines with BOTOX Cosmetic at 64 U can lead to subject satisfaction and natural outcomes.

Estimands

The estimand corresponding to the primary endpoint is as follows:

- The proportion of subjects receiving treatment of BOTOX Cosmetic 64U who achieve the responder status of *Mostly satisfied* or *Very satisfied* on the Facial Line Satisfaction Questionnaire (FLSQ) Item 4 at the Day 30 assessment in the modified intention-to-treat (mITT) population. Subjects who have any intercurrent event resulting in not having a Day 30 assessment will not be included.

The estimand corresponding to the secondary endpoint is as follows:

- The mean change from baseline in subject assessment based on Rasch-transformed score of FACE-Q Psychological Function at the Day 30 assessment for subjects who receive BOTOX Cosmetic 64 U in the MITT population. Subjects who have any intercurrent event resulting in not having a Day 30 assessment will not be included.

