9.0 Efficacy Analyses

9.1 General Considerations

The following considerations apply to all efficacy analyses, unless otherwise specified:

- All efficacy analyses will be conducted in the mITT population unless otherwise specified.
- Day 1 is defined as the day on which the study treatment is first received.

- Baseline for effectiveness parameters will be the last non-missing assessment prior to or on Day 1.
- Study day is always relative to Day 1.
- Change from baseline will be computed as postbaseline minus baseline.
- Continuous variables will be summarized descriptively using number of subjects with observed values (n), mean, standard deviation (SD), median, minimum (min), and maximum (max). In addition, 95% confidence intervals (CIs) will be performed using paired t-tests for change from baseline endpoints.
- Categorical variables will be summarized descriptively using number of subjects with observed values or events (n) and the percentage of subjects with observed values or events.
- Analyses based on responder rates will include a 95% CI for the responder rate using the exact binomial distribution (Clopper-Pearson approach).
- All CIs will be 2-sided 95% CIs, unless stated otherwise.

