9.2 Handling of Missing Data

No imputation of missing data will be made for the efficacy analyses.

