9.3.2 Main Analysis of Primary Efficacy Endpoint(s)

Analysis of the primary endpoint will be conducted based on mITT population. No formal statistical testing will be performed, and descriptive statistics will be tabulated. Observed data will be used without imputation.

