9.3.3 Sensitivity and Supplementary Analyses of the Primary Efficacy Endpoint(s)

Not applicable.

[figure not shown]

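### Does leaving out subjects without a Day 30 assessment make the primary responder rate wrong unless a full-mITT bound stands beside it?

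*SAP*

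**What the plan says.** SAP 4.0 defines mITT by dosing alone: it "includes all enrolled subjects who receive the total dose of 64 U of BOTOX Cosmetic, as described in the study protocol". A Day 30 assessment is not required for membership.

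Protocol 3.1 states the primary estimand as a responder proportion in mITT and then restricts it: "Subjects who have any intercurrent event resulting in not having a Day 30 assessment will not be included". Protocol 7.3 and 7.4 keep to observed data without imputation. SAP 8.0 applies the same rule to the primary endpoint: "subjects who have an intercurrent event resulting in not having FLSQ Item 4 at Day 30 for any reason will not be included". SAP 9.2 adds: "No imputation of missing data will be made for the efficacy analyses".

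On the analysis itself, SAP 9.3.2 says: "No formal statistical testing will be performed, and descriptive statistics will be tabulated". SAP 9.1 attaches an exact (Clopper-Pearson) 95% interval to responder rates and reports the number of subjects with observed values. SAP 9.3.3, the place for sensitivity and supplementary analyses of the primary endpoint, is marked not applicable. SAP 5.0 says: "The number of subjects in each analysis population will also be summarized".

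**The concern.** The estimand names mITT, but the denominator is the part of mITT with a Day 30 answer. Satisfaction is self-reported and open-label, and subjects who stay away could be the less satisfied ones. If so, the observed rate and its lower confidence limit would be too high as a description of everyone given 64 U; if the absent were more satisfied, both would be too low.

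A common safeguard is a supplementary analysis that keeps all mITT subjects in the denominator, and the section where it would sit is empty. With no test in the study, the rate and its interval are the whole primary result. At stake is how far they can be read as describing all treated subjects.

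**Working it through.** **1. The plan's own figure.** Inputs from SAP 2.4: expected rate 75%, n = 100, adjusted logit 95% interval with a correction of -1/2.

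- Centre: ln((75 - 0.5)/(25 - 0.5)) = ln(74.5/24.5) = 1.112
- SE: sqrt(1/75 + 1/25) = 0.2309; times 1.96 = 0.453
- Back-transformed: 65.9% to 82.7%, that is 75 - 9.1 to 75 + 7.7, width 16.8 points

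This reproduces the stated interval. The exact interval planned in SAP 9.1 is slightly wider at 75/100: 65.3% to 83.1%, with a lower arm of 9.7 points.

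**2. Do the documents agree on the denominator?** Protocol 3.1, 7.3 and 7.4 and SAP 8.0, 9.2 and 9.3.2 all lead to observed mITT subjects only. The lists of intercurrent events differ in one item: Protocol 7.3 names not receiving the full 64 U, while SAP 8.0 names not receiving any study drug. Both groups are already outside mITT, so the primary denominator is the same under either list.

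**3. How far could the observed rate be from the full-mITT rate?** Let p be the observed rate and m the fraction of mITT without Day 30 data.

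- Worst case (all missing are non-responders): p(1 - m), so overstatement is at most pm
- Best case (all missing are responders): p(1 - m) + m, so understatement is at most (1 - p)m

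Whatever p is, neither shift can exceed m. The documents give no value for m, so the rows below are illustrative: 100 fully dosed subjects and about 75% response among those observed.

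| Missing | Observed rate (exact 95% CI) | Worst case | Best case | Max. overstatement | Max. understatement |
|---|---|---|---|---|---|
| 2 | 74/98 = 75.5% (65.8 to 83.6) | 74.0% | 76.0% | 1.5 | 0.5 |
| 4 | 72/96 = 75.0% (65.1 to 83.3) | 72.0% | 76.0% | 3.0 | 1.0 |
| 8 | 69/92 = 75.0% (64.9 to 83.4) | 69.0% | 77.0% | 6.0 | 2.0 |
| 12 | 66/88 = 75.0% (64.6 to 83.6) | 66.0% | 78.0% | 9.0 | 3.0 |

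If half of the missing subjects were satisfied, the overstatement would be 0.5, 1.0, 2.0 and 3.0 points; for 4 missing, 75.0 - (72 + 2) = 1.0.

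**4. When does the worst case leave the reported interval?** From 1 to 13 missing it stays inside. At 14 it depends on the count: 64/86 has lower limit 63.9% against a worst case of 64.0% (inside), while 65/86 has 65.1% against 65.0% (outside). At 15, 64/85 has 64.7% against 64.0% (outside). Against the planning limit, 0.75(1 - m) < 0.659 requires m above about 12%.

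**5. Can a reader get the bounds from planned output?** Let N be the mITT size (SAP 5.0), n the number observed and x the number of responders (both SAP 9.1). The worst case is x/N and the best case is (x + N - n)/N. For 4 missing: 72/100 = 72.0% and (72 + 100 - 96)/100 = 76.0%. All three counts are planned.

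**6. What would change?** The primary rate and its exact interval stay as they are with or without the extra row. There is no success criterion for a bound to overturn.

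**The case for a change.** The strongest contrary case is that in a descriptive study the primary rate is the result, so its robustness should be shown on the page. Deriving the bounds means combining figures from separate tables, and no interval is planned for either bound. SAP 5.0 tabulates reasons for leaving the study, but Protocol 7.3 also foresees subjects who continue and merely miss Day 30, and the visible text plans no summary of their reasons. At 12 missing the worst case is 9.0 points lower, about the size of the 9.1-point lower arm in SAP 2.4. A bound needs no assumption about who is missing, and the data are already collected.

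Much of this stands as fact. The visible text plans no all-mITT row. The text under SAP 3.3 and 9.5 is not available in the public copy, so the absence cannot be confirmed there, though SAP 9.2 and 9.3.3 make a hidden bound unlikely. A reviewer may reasonably prefer to see the row.

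It does not show a defect. The high-missing rows have no support in the documents. The plan also limits missing data: Day 30 is the first follow-up visit (SAP 2.2), planned extended absence is an exclusion (Protocol 5.1, criterion 27), calls and a certified letter precede loss to follow-up (Protocol 5.5), and subjects are otherwise followed at all visits (Protocol 5.6). An all-mITT analysis would also score unrelated missed visits, such as those due to COVID, as non-response. It could not simply be added in SAP 9.3.3 either, because Protocol 7.3 and 7.4 and the exclusion clause in SAP 8.0 say otherwise.

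**Conclusion.** The concern does not hold. Observed-case handling is the declared estimand, applied consistently, and the planned rate and exact interval estimate what the protocol defines. No test, threshold or comparator depends on them, and the worst- and best-case rates can be computed from planned counts.

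With 2 to 4 of 100 missing and about 75% response, the most extreme overstatement is 1.5 to 3.0 points, well inside the exact interval; the worst case leaves that interval only at about 14 to 15 missing. These sizes rest on an assumed missing count, an assumed 100 fully dosed subjects and the 75% planning rate. Bias from missing assessments is possible, but nothing in the documents establishes it. What remains is a preference for an additional supplementary row.

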4 INVESTIGATIONAL PLAN

4.1 Overall Study Design and Plan

This is a 6-month, prospective, multicenter, open-label study to evaluate subject satisfaction and natural outcomes following the administration of BOTOX Cosmetic 64 U for the treatment of upper facial lines.

The study will enroll approximately 100 subjects with moderate to severe GL, LCL, and FHL as assessed by the investigator. Out of the approximately 100 enrolled subjects:

- approximately 20% of the study population will be treatment naïve to any botulinum toxin of any serotype for any indication,
- approximately 20% of the study population will be self-identified as male,

- approximately 20% of the study population will be self-identified as Asian, and
- approximately 20% of the study population will have Fitzpatrick skin phototypes of IV, V, or VI.

A review of individual site data will be conducted once a sufficient number of subjects has been enrolled. The site will be permitted to enroll additional subjects upon sponsor approval. This process may be repeated as needed.

On Day 1, after subjects are verified to meet all eligibility criteria and have completed all baseline study procedures, they will receive 64 U of BOTOX Cosmetic. Each subject will receive a total of 16 injections (0.1 mL or 4 U of BOTOX Cosmetic per injection), with 5 injections in the glabellar complex, 3 injections in each of the lateral canthal area (6 total injections), and 5 injections in the frontalis muscle.

There are seven in-clinic visits: screening/baseline/treatment (Day 1), post-treatment follow-up visits (Days 30, 60, 90, 120, 150), and study exit (Day 180 or Early Exit). The study schema of the study is shown in [Figure 1](#).

Further details on study procedures are located in the Operations Manual ([Appendix E](#)).

Figure 1. Study Schema

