7.4 Statistical Analyses for Efficacy

Summary and Analysis of the Primary Endpoint

Analysis of the primary endpoint will be conducted based on mITT population. No formal statistical testing will be performed, and descriptive statistics will be tabulated. Observed data will be used without imputation.

Summary and Analysis of Secondary and Additional Endpoints

Analysis of the secondary and additional endpoints will be conducted based on mITT population. Descriptive statistics will be tabulated and observed data will be used without imputation.

Additional details will be provided in the SAP.

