14.0 Version History

SAP Version	Date	Summary
1.0	14 March 2024	Initial version
2.0	17 March 2025	
Section 3.3
 
Added 3 additional endpoints:
Responder status of Mostly satisfied or Very satisfied on the Facial Line Satisfaction Questionnaire (FLSQ) Follow-up Item 4 at all follow-up visitsChange from baseline in subject's assessment based on Rasch-transformed score of FACE-Q Psychological Function scale at all follow-up visitsAchievement of ≥ 20 points improvement from baseline on FLSQ impact domain score at all follow-up visits 
Section 6.0
 
Updated study drug duration analysis grouping 
Section 7.1
 
Added 'prior Botulinum Toxin Treatment' in demographic variable list 
Section 9.1
 
Stated '95% confidence intervals (CIs) will be performed using paired t-tests for change from baseline endpoints' and 'Analyses based on responder rates will include a 95% CI for the responder rate using the exact binomial distribution (Clopper-Pearson approach).' 
Section 9.5
 
removed 'Listings of all endpoint values will also be provided.' Only listings for primary and secondary endpoints will be provided.updated 'Onset of efficacy as measured by subject self-assessment in a patient electronic diary from Day 1 up to Day 14' to 'Onset of efficacy as measured by subject self-assessment in a patient electronic diary from Day 2 to Day 15' per protocol V3.0added Kaplan-Meier language for endpoint 'Onset of efficacy as measured by subject self-assessment in a patient electronic diary from Day 2 to Day 15.'Added 3 additional endpoints:

		
○ Responder status of Mostly satisfied or Very satisfied on the Facial Line Satisfaction Questionnaire (FLSQ) Follow-up Item 4 at all follow-up visits○ Change from baseline in subject's assessment based on Rasch-transformed score of FACE-Q Psychological Function scale at all follow-up visits○ Achievement of ≥ 20 points improvement from baseline on FLSQ impact domain score at all follow-up visits 
Section 9.6
 
• added subgroup analyses for primary and secondary endpoint by toxin naïve, sex, race and Fitzpatrick skin type
--	--	--

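### Does the plan leave open which satisfaction answers count at Days 60 to 180?

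*SAP*

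**What the plan says.** SAP 8.0 covers the primary and secondary endpoints, both at Day 30. A subject with an "event resulting in not having FLSQ Item 4 at Day 30 for any reason will not be included in the primary efficacy endpoint", and the secondary analysis follows the same approach. Protocol 7.3 is likewise written around the Day 30 assessment.

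The later visits enter through SAP 14.0, which records that version 2.0 added responder status on the "Facial Line Satisfaction Questionnaire (FLSQ) Follow-up Item 4 at all follow-up visits", with a matching FACE-Q endpoint. The same log narrows the listings: "Only listings for primary and secondary endpoints will be provided".

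For endpoints beyond the primary, Protocol 7.4 says that analysis of secondary and "additional endpoints will be conducted based on mITT population. Descriptive statistics will be tabulated and observed data will be used without imputation". SAP 9.2 agrees: "No imputation of missing data will be made for the efficacy analyses". SAP 9.1 sets mITT as the population for all efficacy analyses and adds "Study day is always relative to Day 1".

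Protocol 4.1 describes the visits after treatment as "post-treatment follow-up visits (Days 30, 60, 90, 120, 150), and study exit (Day 180 or Early Exit"). Protocol 5.5 directs every subject who wishes to leave, or who is discontinued on whatever ground, to the Early Exit procedures. Protocol 5.6 keeps subjects on the scheduled visits except where consent is withdrawn. Protocol 5.4 leaves it to the investigator or sponsor whether a subject who used a prohibited treatment is discontinued.

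**The concern.** The endpoints were extended past Day 30, and the visible intercurrent-event rules were not. Three things then seem open.

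- **Which row an exit answer belongs to.** Early Exit shares a visit with Day 180 and can happen on any day. If answers are sorted by visit name, one given at Day 70 could be tabulated as Day 180.
- **Who goes to Early Exit.** Protocol 5.5 and 5.6 give different answers for some leavers, so the same event could produce different later data at different sites.
- **What a late answer measures.** The hypothesis in Protocol 3.1 is about a single treatment. A dissatisfied subject who obtains toxin elsewhere and then reports satisfaction would count as a responder under the observed-data rule.

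At stake is how the late rows are read, in a study without a control arm. Non-study toxin is conceivable: Protocol 4.1 plans that "approximately 20% of the study population will be treatment"-naïve, which leaves about 80 of 100 with earlier exposure, and no retreatment is offered for 180 days. Listings would not help, since the listed endpoints are the Day 30 ones.

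**Working it through.** **1. The plan's own figure.** Inputs from SAP 2.4: n = 100, expected rate 75%, correction −1/2, 95% two-sided.

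- Centre: ln[(75 − 0.5)/(25 − 0.5)] = ln(74.5/24.5) = 1.1121.
- Standard error: √(1/75 + 1/25) = 0.2309.
- Limits after back-transformation of 1.1121 ± 1.96 × 0.2309: 65.9% and 82.7%, that is −9.09 and +7.70 points, width 16.79.

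The stated 16.8% is reproduced. It concerns Day 30, and nothing below alters it.

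**2. Early Exit answers placed in a Day 180 row.** The number of exits e and the 50.0% rate among completers are assumptions. With s satisfied completers, the row runs from s/100 (no exit satisfied) to (s + e)/100 (all satisfied).

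| e | Completers | Their Clopper-Pearson interval | Row with exits added |
|---|---|---|---|
| 4 | 48/96 = 50.0% | 39.6% to 60.4% | 48.0% to 52.0% |
| 10 | 45/90 = 50.0% | 39.3% to 60.7% | 45.0% to 55.0% |
| 20 | 40/80 = 50.0% | 38.6% to 61.4% | 40.0% to 60.0% |

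Even the extremes stay inside the interval that would be printed for completers alone. If 20% of 10 exits are satisfied, the row is (45 + 2)/100 = 47.0%, a shift of 3 points.

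**3. Answers after non-study toxin.** Assume S of 100 would be satisfied without further treatment, and that k dissatisfied subjects take toxin and all become satisfied. Observed: (S + k)/100. Left out: S/(100 − k). Scored as non-response: S/100.

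| S | k | Observed | Left out | Non-response |
|---|---|---|---|---|
| 50 | 1 | 51.0% | 50.5% | 50.0% |
| 50 | 5 | 55.0% | 52.6% | 50.0% |
| 50 | 10 | 60.0% | 55.6% | 50.0% |
| 50 | 20 | 70.0% | 62.5% | 50.0% |
| 75 | 1 | 76.0% | 75.8% | 75.0% |
| 75 | 5 | 80.0% | 78.9% | 75.0% |
| 75 | 10 | 85.0% | 83.3% | 75.0% |
| 75 | 20 | 95.0% | 93.8% | 75.0% |

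At S = 75 and k = 10, the observed 85/100 has a Clopper-Pearson interval of 76.5% to 91.4%, which lies above 75.0%. That case needs 10 of the 25 dissatisfied subjects to obtain toxin against protocol and every one of them to be satisfied afterwards; k = 20 needs 20 of 25. It also carries the Day 30 planning rate over to a late visit. No document supports these counts.

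**4. The passages side by side.**

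- *Default.* Protocol 7.4 names additional endpoints when it states the observed-data rule. Answers after non-study toxin therefore have a treatment: they count.
- *Row.* Protocol 4.1 separates the follow-up visits (Days 30 to 150) from study exit. The log speaks of follow-up visits, so on a literal reading there may be no Day 180 row. Whether FLSQ is completed at Early Exit cannot be seen either.
- *Windows.* SAP 9.1 defines study day, so each dated answer can be assigned by day. SAP 9.5 held method text (the log mentions Kaplan-Meier wording), but it is blank in the public copy, as is SAP 3.3. The activity tables and the Operations Manual are not shown.
- *Routing.* Protocol 5.5 and 5.6 agree when consent is withdrawn. They disagree only for a subject discontinued without that.

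**The case for a change.** The strongest case for a change is that observed data settles whether an answer is used but not which row it enters, and the shared visit name invites the wrong row. The protocol also treats outside treatment as confounding before Day 1: Protocol 4.2 requires washout, and criterion 20 bars toxin for 6 months. The visible analysis rules have no counterpart after Day 1. The remedy would be one paragraph and no new data.

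Part of this stands. The windowing question is fair to put to the sponsor, and so is whether late answers given after non-study toxin or a prohibited facial procedure will be counted by visit. The conflict between Protocol 5.5 and 5.6 is in open text, and no hidden section removes it.

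The rest does not carry. A rule that may sit in blanked text cannot be reported as absent. Scoring answers after toxin as non-response is one estimand; using them as observed is another, and it is defensible for a descriptive additional endpoint. Asking the sponsor to say that observed answers are kept largely repeats Protocol 7.4. The exposure argument is also weaker than it looks, because criterion 25 excludes anyone expecting to need toxin and criterion 20 means that experienced subjects have already gone 6 months without it. Nor is the reader left blind: SAP 7.2 to 7.4 tabulate concomitant medications and concurrent procedures and count deviations, which gives an approximate overall k, though not one by visit.

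**Conclusion.** No change to the analysis plan follows. The visit assignment is at most a detail that analysts fill sensibly, by placing a dated exit answer by study day, and it may already be written in text that is not public. Using late answers as observed is a stated default and a fair trade-off.

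The disagreement between Protocol 5.5 and 5.6 is real but narrow. It concerns a subject discontinued by the investigator or sponsor who has not withdrawn consent. The two passages must be reconciled, which is a matter of wording and alters no Day 30 result and no stated figure.

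The size of any effect on later visits is unknown. One affected subject moves a rate by at most about 1 point. The larger shifts shown rest on assumed counts and on every affected subject answering the same way. They apply to additional, descriptive rows for which SAP 13.0 plans no test, in a study whose primary and secondary endpoints are at Day 30 and whose objective in Protocol 3.1 does not mention duration. The conclusion rests on the public copy: if the full SAP 9.5 turned out to assign exit answers by visit name, the windowing question would need another look.
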